There needs to be one mixed assignment zone (Boto), which will primarily be a non-PBO distribution (see Table). For reasons of study power (below) it is crucial to organise the distribution such that the net types cluster around health centres used for assessment, to ensure that the zone can be retained as a cluster for at least one and hopefully both LLIN types in the study. The number of available PBO LLINs represents just under 25% of the total net need for Boto. As a result of logistical considerations and also to reduce the potential for mosquito dispersal between clusters with different types of LLIN a distribution plan to a cluster of western aires de sante is proposed for Boto (Figure 7).

Figure 7. Map of Boto health zone showing the western areas of Bomele, Bombili, Bobandu and Bokozo proposed to receive PBO LLINs (blue); all other areas will received standard LLINs. ?-1,2 show uncertain boundary locations between zones

If projected LLIN needs for each of the four areas are accurate, this would leave 2,000 surplus PBO LLINs, which could be distributed as close as possible, i.e. preferably along borders of these aires de sante to expand the size of the PBO-LLIN cluster.

More generally the mixed distribution in Boto could provide an important template for future distributions to provinces where division into fewer zones would preclude a statistically-useful comparative study if LLINs of contrasting types were distributed solely at the zonal level. Whilst statistically a distribution fully randomized at the level of aires de sante would be powerful, this is logistically challenging, may lack visible mapped impact on a malaria data map. Grouping of aires de sante - in the way proposed for Boto - could provide a viable intermediate distribution plan to meet statistical requirements, and, in addition to relative logistical ease also has the advantage of reducing the impact of human, net and mosquito movements among net-type clusters.

Proposal hypotheses and endpoints

Epidemiological

Primary

Hypothesis: PBO LLIN distribution will result in a lower malaria prevalence than standard (non-PBO) LLINs as indicated by reduced prevalence in ANC1 visitors.

Endpoint: monthly malaria prevalence in ANC1 visitors measured using RDTs, with main assessment points at 6 monthly intervals and intermediate assessments quarterly.

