Sample size calculation and power: From preliminary analyses it was evident that a minimum 8 vs 8 cluster/ arm trial would be required to adequately power the study to detect plausible effect sizes using a relatively simple cluster arm comparison for a single month's data (temporal variation is unknown so it is difficult to include multiple months in *a priori* power analysis). We used fixed assumptions for the number of available health centres/ zone of N=7 and number of ANC1 visitors

per month of N=20, giving a cluster size of N=140. Note that varying the cluster size has only a moderate impact on power, provided health centres are chosen randomly from those available. Parameter values for the inter-cluster coefficient of variation (*k*, which has a large impact on power) were estimated from DHIS2 2018 data from the rate of positive malaria tests per month per capita (i.e. data divided by population size of zone) as a proxy. Following equation 9 in Hayes & Bennett (1999) we calculated k=0.18 from these data. However, noting this is lower than estimated from the only comparable published study from Tanzania (k values of 0.20-0.28 depending on survey round; West et al. 2014) we also examined a 'high COV' value of k=0.3.

Similarly we lacked information on the baseline prevalence of malaria for Sud Ubangi, with the last survey in 2013-14 detecting a rate of 24% in children under 5 (MPSMRM 2013-14), which using a conversion factor of 1.44 between child and pregnant women's prevalences (van Eijk et al. 2015) we used to estimate an ANC prevalence value of 17%, which is also very close to the average figure for the DRC ANCs presented in Hellewell et al. (2018). However, figures in Hellewell vary greatly and thus because of the considerable uncertainty in this point estimate, we examined a range of possible prevalence rates (applicable to the standard-LLIN reference arm).

We identified the minimum detectable reduction in prevalence using equation 4 from Hayes & Bennett (1999) with the following study design parameters:

Arms=2; Clusters (zones)/arm = 8; subjects/ cluster = 140; k = 0.11 or 0.30; α =0.05; power =80%; prevalence in reference standard-LLIN arm (π 0) varied between 5 and 50%

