All data will be analysed primarily on the basis of intention-to-treat. The primary outcome will be the prevalence of parasitaemia from the ANC visitor surveys, which will be compared between treatment arms using generalized linear Poisson mixed models with log link function to allow assessment of intra-cluster correlation, and correction factor to maintain type I error rate with a small number of clusters, but maintain power for the number of clusters in our study (Leyrat et al. 2017). Continuous (monthly) data will be available for each major endpoint analysis and will be analysed with time since LLIN distribution as a covariate. However, the power analysis above is based on separate monthly assessments. Interim endpoint analyses will be conducted quarterly, to allow ongoing assessment of the trial by funders. Meaningful baseline data will not be available for the study and therefore it is not intended to perform adjusted analyses *a priori*, though if systematic differences in influencing factors are identified, covariates may be incorporated into analyses. Blinding at the level of data collection is not possible because of the ready identifiability of the different types of LLINs. However, data source will be encoded prior to statistical endpoint analysis to ensure blinding.

Entomological

Primary

Hypothesis: PBO LLIN distribution will reduce the benefit of P450 metabolic-based enzymes and arrest selection on a key genomic area for resistance leading to lower frequencies in PBO-LLIN zones (via stasis or a fall) than observed in zones with standard LLINs (in which an increase is expected). In lay terms this is testing a hypothesis that PBO LLINs will reverse the increase in pyrethroid resistance; an effect which we should be able to capture using informative DNA markers for molecular surveillance.

Endpoint: comparative annual resistance marker frequency in *An. gambiae* measured using molecular surveillance diagnostics

Sample size calculation and power:

Entomological indices can be readily assessed at intervals with a periodicity of 6 months suggested as providing a good timeframe for a hypothesised change in marker frequencies. The work is

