powered however for a 12-month comparison which it is anticipated would come from comparisons of collections made initially at 0 vs 12 months, but with additional comparisons (subject to study continuation) at 6 vs 18 months etc. We base calculations on a current base resistance marker frequency (the Cyp6 gene-cluster marker haplotype described above) of 0.72, which is based on recent local data we have obtained. A projected 5% annual decrease in the PBO arm and 5% increase in the standard LLIN arm, translates into a projected difference between arms of approximately 10% per year. The total number of *An. gambiae* required per collection period to detect such a difference as significant (using an exact test) is N=1392 (allowing a two-fold higher collections in standard-LLIN houses than PBO-LLIN houses). Clustering is not accounted for in the analysis because we postulate (based on general patterns for the species) that it is unlikely there will be significant *a priori* population genetic structure within the *An. gambiae* population of Sud Ubangi.

Allowing for 16% non-*An. gambiae* in collections (based on our data from neighbouring Nord Ubangi province; Lynd et al. 2018) equates to a total of 1,650 Anopheles per survey period. Allowing for an average catch of N=3 *An. gambiae* per standard-LLIN house, and 1.5 in PBO LLIN houses this would require a total number of N=734 houses to be sampled by prokopack collections during each collection around the 6 month periods. We will sample from 4 clusters per arm to reduce travel costs and time). Specifically, we will sample from 3 separate health zones per arm and then from both PBO- and standard-LLIN clusters within the mixed Boto health zone. Villages to be sampled will be those in close proximity to the health centres included in the epidemiological component of the study.

It is intended that the same houses would be sampled each time, though if this is not possible, or if verbal consent to access to sample is not provided a neighbouring replacement house would be recruited. The projected 10% decrease is annual and therefore the main comparisons would compare surveys separated by 12 months, i.e. months 0 vs 12, 6 vs 18, 12 vs 24, etc.

Secondary entomological outcomes

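### The primary hypothesis is spread over several co-equal main assessment points plus quarterly interim analyses, and no single analysis is named to decide it at 5%

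*Protocol*

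**What the plan says.** Under Proposal hypotheses and endpoints (Epidemiological, Primary), the single hypothesis is that "PBO LLIN distribution will result in a lower malaria prevalence than standard (non-PBO) LLINs". The endpoint is monthly prevalence by RDT in ANC1 visitors, "with main assessment points at 6 monthly intervals and intermediate assessments quarterly". The main points are plural, and none is ranked above the others.

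The sample size section sizes the trial "using a relatively simple cluster arm comparison for a single month's data", and its design parameters include "α =0.05; power =80" (the last figure in per cent).

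The epidemiological Data analysis section makes three relevant statements:
- On looks during the trial, it announces repeated analyses for an outside audience: "Interim endpoint analyses will be conducted quarterly, to allow ongoing assessment of the trial by funders".
- On how the data enter the model, it points to all months together and to more than one major analysis: "Continuous (monthly) data will be available for each major endpoint analysis and will be analysed with time since LLIN distribution as a covariate".
- On the basis for the sample size, it concedes a difference from that model: "However, the power analysis above is based on separate monthly assessments".

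That section mentions type I error once, for a correction suited to a small number of clusters.

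**The concern.** Alpha is calibrated to one comparison, while the plan schedules many comparisons of the same hypothesis. A small-cluster correction makes each test honest by itself; it does nothing about repeated looks. Two consequences follow. First, if superiority may be claimed at any main or interim point that crosses 0.05, the error rate of the claim exceeds 5%. Second, even with no such intent, the protocol cannot say whether the trial succeeded if the six-monthly results disagree, which is plausible as nets age.

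The Aim and approach section expects donors to use the results in near-term net choices, puts the extra cost of PBO nets in this province at $650k, and offers the design as a possible template. The deciding analysis should therefore be unambiguous.

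**Working it through.** **Inputs from the protocol.** 8 zones per arm; 140 women per zone per month (7 centres × 20); reference prevalence 17%; alpha 0.05 (sidedness not stated, two-sided assumed); between-zone coefficient of variation k. The protocol calculates k = 0.18 but lists 0.11 and 0.30 as design parameters, so all three are used.

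**Assumed.** Epidemiological follow-up is not given in the text (the timeline is in a separate file). I use 12, 24 and 36 months; household mosquito sampling allows up to 6 six-monthly rounds. Month-to-month correlation of zone effects is also not given; the main case takes them as constant.

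**Variance components at k = 0.18.**
- Between zones: (0.18 × 0.17)² = 0.000936.
- Binomial, one month: 0.17 × 0.83 / 140 = 0.001008.
- Zone share: 0.000936 / (0.000936 + 0.001008) = 0.48 for one month; with three months, 0.000936 / (0.000936 + 0.000336) = 0.74.

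Looks are therefore correlated, and the independence formula 1 − 0.95ⁿ (18.5% for 4 looks, 33.7% for 8) is only an upper reference.

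**Reproducing the stated alpha.** One single-month t-test on 8 vs 8 zone summaries (14 df) under no effect rejects in 5.0% of simulated trials.

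**Repeated looks.** 20,000 null trials per setting; a trial counts if |t| exceeds the 14-df 5% critical value at any look.

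Each look uses all months accumulated so far, stable zone effects:

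| Follow-up (months) | k | Six-monthly looks | Quarterly looks |
|---|---|---|---|
| 12 | 0.11 / 0.18 / 0.30 | 7.1 / 6.4 / 5.9% | 9.2 / 8.0 / 7.0% |
| 24 | 0.11 / 0.18 / 0.30 | 8.3 / 7.4 / 6.3% | 11.2 / 9.2 / 7.1% |
| 36 | 0.11 / 0.18 / 0.30 | 9.2 / 7.6 / 6.7% | 11.7 / 9.4 / 7.8% |

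Each look uses one month's data only, stable zone effects:

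| Follow-up (months) | k | Six-monthly looks | Quarterly looks |
|---|---|---|---|
| 24 | 0.11 / 0.18 / 0.30 | 17.7 / 15.8 / 13.1% | 31.3 / 27.1 / 19.4% |

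If zone effects drift (month-to-month correlation 0.9, assumed), accumulating quarterly looks reach up to 17% at 36 months.

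**Direction.** These counts are two-sided. At k = 0.18 with accumulating quarterly looks, false crossings favouring PBO are about 4-5%, against a nominal 2.5%.

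**Effect of the fix on power.** The Hayes and Bennett formula is c = 1 + (1.96 + 0.84)² × [(π₀(1−π₀) + π₁(1−π₁))/m + k²(π₀² + π₁²)] / (π₀−π₁)². At m = 140, k = 0.18 and π₁ = 0.17 × (1 − 0.344) = 0.1115, c = 1 + 7.849 × (0.001716 + 0.001339) / 0.003420 = 8.0. The detectable reduction at alpha 0.05 is thus 34.4% (29.8% at k = 0.11, 44.2% at k = 0.30).
- One test on one month's data at 0.05: unchanged.
- Four confirmatory points with Bonferroni (0.0125 each): 34.9%, 40.2% and 51.3% for k = 0.11, 0.18 and 0.30.
- One test pooling 24 months (m = 24 × 140 = 3,360) with stable zone effects: about 24.5% at k = 0.18. Check: π₁ = 0.1284 and c = 1 + 7.849 × (0.000075 + 0.001470) / 0.001735 = 8.0.

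**The case against.** **Unadjusted testing is inferred.** Alpha 0.05 appears only among the sample-size parameters. No passage gives a threshold per look or says that any crossing counts as success, and interim boundaries are commonly left to a SAP, which is not at hand. This stands, and it makes every inflation figure conditional. It does not remove the point: the timing of the primary endpoint is protocol content, and the protocol itself fixes it as several equal points.

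**The larger figures rest on the weaker reading.** The analysis section describes continuous monthly data with time as a covariate, which most naturally means accumulating data in one model. The remark about separate months describes the basis for power. This also stands, so 6-12% is the main figure and 13-31% the alternative. A reader might infer that the error rate is far above 5% whatever the reading; the documents do not establish that.

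**Result-dependent stopping.** A reader might infer that the trial can stop on a favourable ANC result, because funders see quarterly analyses and the protocol says "with additional comparisons (subject to study continuation) at 6 vs 18 months etc". That phrase concerns the mosquito resistance-marker comparisons. Nothing links continuation to ANC efficacy results and no stopping rule is given, so this is at most a risk.

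**Repeated assessment serves a stated aim**, the relative benefit of PBO nets over the net life cycle. That is right, and the fix keeps those estimates. It does not require each of them to be a confirmatory test.

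**Conclusion.** The point holds as a defect in how the primary inference is fixed: one hypothesis, several main points, quarterly interim endpoint analyses, and no analysis that decides. No single inflation figure follows from the document, because the number of looks, the follow-up and the stability of zone effects are not stated. With 0.05 used at each look and stable zone effects, the two-sided chance of at least one false-positive look is about 6-12% for accumulating data (12-36 months, k 0.11-0.30). It is about 13-31% for separate single months over 24 months. Roughly half of these would be false claims for PBO. Every multi-look setting examined exceeds 5%, though only modestly on the best-supported reading. Interim looks used purely for reporting would do no harm beside one named final test, but none is named.

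**What to change.** In the endpoint and Data analysis sections, name one confirmatory analysis: the arm prevalence ratio from the planned mixed model, with its small-cluster correction, over all post-distribution months to one pre-stated end point (for example month 24), tested once at two-sided 0.05. State that the six-monthly results are arm-by-period estimates with confidence intervals from the same model, reported for the net life-cycle aim and not as separate tests of the hypothesis. Keep the quarterly funder reports descriptive. If a decision may follow from them, state an alpha-spending function (O'Brien-Fleming type, for example) and the number of looks.

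The cost is protocol wording and the loss of an early significance claim. A single pooled test does not worsen the detectable reduction and improves it if zone effects are stable, whereas splitting alpha over four confirmatory points would raise it from 34.4% to 40.2% at k = 0.18.

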implication of which for them is shown in the flow diagram below, i.e. they will be tested for malaria whether symptomatic or not. It will be made clear that there is no accepted benefit of either, and that the option is being offered solely for the purposes of our LLIN evaluation study. If, after asking any questions and discussing with friends or relatives as desired, they agree and sign the consent form, they will proceed via the lower route shown in the figure. If they do not wish to be included they will follow the route shown in the upper part of the diagram, which represents standard care. The decision will need to be taken within the timeframe of the appointment, and if a clear and certain decision is not reached by this time the standard care route will be followed.

Inclusion of health centres (aires de sante) in the study

The aires de sante (N=7) from each zone de sante (N=16) to be included in the study will be identified by random allocation from a list of functional aires de sante in a zone with >20 ANC1 visitors per month based on 2018 DHIS2 data.

Data collection and collation

Data collection should start at the first possible ANC before or just after (determined by RDT/ACT supply and training logistics) LLIN distribution. Recordings preceding the distribution would be beneficial but are unlikely to be feasible owing to time constraints.

It is proposed that study RDT results are recorded separately on the questionnaire form (appended) and transferred to the ANC register (observations section), rather than as a suspected or tested case in the standard register, which is the current procedure. The simple questionnaire will collect only essential information about the participant and their home environment as pertains to malaria risk and should be readily completed within the time waiting for the RDT result. Variables generated from the questionnaire data may serve as covariates in analyses although this is not planned *a priori*. ACT treatment would be administered to women testing positive in the RDTs. Data collected will be transferred monthly to Gemena in the same way as the DHIS2 data collation process, and passed to the study epidemiological coordinator.

Training

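### The primary power calculation leaves out the variance from sampling 7 health centres per zone, so its detectable reductions are optimistic by an amount the protocol does not fix

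*Protocol*

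**What the plan says.** All references are to the Protocol.

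- **Sample size calculation and power (Epidemiological, Primary).** The design is "Arms=2; Clusters (zones)/arm = 8". The within-zone sample is built up as "We used fixed assumptions for the number of available health centres/ zone of N=7" and 20 first-visit women per centre per month, "giving a cluster size of N=140". The minimum detectable reduction comes from equation 4 of the cited cluster-trial paper, with 80% power, α=0.05 and k entered as 0.11 or 0.30.
- **Source of k, same section.** The estimate of 0.18 comes from positive tests per month per capita, "data divided by population size of zone) as a proxy". A higher value of 0.30 was added because a Tanzanian study gave 0.20–0.28.
- **Inclusion of health centres.** The 7 centres "from each zone de sante (N=16) to be included in the study will be identified by random allocation" from functional centres with more than 20 first visits per month.
- **The only remark on centre sampling.** The sample size section says that cluster size affects power only moderately as long as centres are picked at random. It gives no between-centre CV, intraclass correlation or design effect.
- **Conclusions drawn.** The text introducing Figure 8 says that, if the lower k is realistic, the study is well placed to detect the smaller Tanzanian effect. The Epidemiology design summary says the design should be robust to parameters not yet known, provided the effect is of the Tanzanian order.

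**The concern.** The sampling has two stages, centres within a zone and then women within a centre, but the formula has one. Its within-zone term is p(1−p)/140, which treats the 140 women as a simple random sample of the zone's antenatal attenders. If prevalence differs between centres and only some centres are drawn, the zone estimate also carries the error of which 7 were drawn. A k computed from whole-zone counts measures real differences between zones and cannot contain that error.

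The remark about random choice does not close the gap. Random choice makes the 7 centres representative on average, but their mean still varies around the zone mean.

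At stake are the detectable reductions in Figure 8, the favourable statement based on the lower-k curve, and the robustness sentence. That sentence claims cover for unknown parameters, yet this unknown parameter was never varied.

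**Working it through.** **Inputs from the protocol.** c=8 zones per arm; n=7×20=140; reference prevalence p0=0.17 (24%/1.44=16.7%, which the protocol gives as 17%); k=0.11 and 0.30 as entered, and 0.18 as estimated; α=0.05; power 80%.

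**Assumptions.** α is two-sided. The protocol names the equation without printing it, so I take the standard one-level form for proportions. The between-centre CV within a zone (kc) is not given and is shown from 0.1 to 0.5. The number of eligible centres per zone (M) is not in the text and is shown as large, 15, 10 and 7.

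**Formula.** c = 1 + (1.960+0.842)² × [p0(1−p0)/n + p1(1−p1)/n + k²(p0²+p1²)] / (p0−p1)², solved for p1. The detectable reduction is 1−p1/p0.

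**Step 1: the plan's calculation.** The text states no numerical detectable reduction and the values plotted in Figure 8 could not be checked, so this is the formula's output. For k=0.11 the solution is p1=0.1194. The bracket is 0.001008+0.000751+0.000522=0.002281, (p0−p1)²=0.002558, and 1+7.849×0.002281/0.002558=8.0. The reduction is 29.8%. In the same way k=0.18 gives 34.4% and k=0.30 gives 44.2%.

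**Step 2: add the centre stage.** The mean of 7 centres drawn from M has extra relative variance kc²(1−7/M)/7, so k² becomes k² + kc²(1−7/M)/7. Example with k=0.11, kc=0.5 and M large: 0.0121+0.25/7=0.0478. Then p1=0.1064, the bracket is 0.001008+0.000679+0.001923=0.003610, (p0−p1)²=0.004048, and c is again 8.0. The reduction is 37.4%.

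**Step 3: detectable reduction (%) at p0=17%.**

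| k | M | kc=0 | 0.1 | 0.2 | 0.3 | 0.5 |
|---|---|---|---|---|---|---|
| 0.11 | large | 29.8 | 30.1 | 31.2 | 32.8 | 37.4 |
| 0.11 | 15 | 29.8 | 29.9 | 30.5 | 31.4 | 34.2 |
| 0.11 | 10 | 29.8 | 29.9 | 30.2 | 30.7 | 32.3 |
| 0.18 | large | 34.4 | 34.7 | 35.6 | 37.0 | 40.9 |
| 0.18 | 15 | 34.4 | 34.6 | 35.0 | 35.8 | 38.1 |
| 0.18 | 10 | 34.4 | 34.5 | 34.8 | 35.2 | 36.5 |
| 0.30 | large | 44.2 | 44.4 | 45.0 | 46.0 | 48.9 |
| 0.30 | 15 | 44.2 | 44.3 | 44.6 | 45.1 | 46.8 |
| 0.30 | 10 | 44.2 | 44.2 | 44.4 | 44.7 | 45.7 |

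With M=7 the added term is zero and each row keeps its kc=0 value.

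**Step 4: power at the kc=0 detectable reduction, M large, for kc=0.1 / 0.3 / 0.5.** k=0.11: 79 / 71 / 58%. k=0.18: 79 / 73 / 63%. k=0.30: 80 / 76 / 70%.

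**Step 5: headroom in k=0.30, M large.** The kc that raises a true zone k to 0.30 is √[7(0.30²−k²)]. For k=0.18 this is √(7×0.0576), about 0.63. For k=0.28 it is √(7×0.0116), about 0.28.

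**The case against.** **The size is not known.** This stands. At a between-centre CV of 0.1 the change is 0.3 points or less, and at 0.2 it is at most 1.4 points. A reader might infer from the lowest power figure, 58%, that the study is materially underpowered. The documents do not support that. The figure needs k=0.11, a CV of 0.5 and 7 centres as a negligible share of the eligible list, all at once. The section on ante-natal clinic data treats 7 as a minimum number of suitable centres, so in some zones 7 may be much of the list. The entry of k=0.11 also conflicts with the 0.18 that the same section says was calculated, which is a separate matter to reconcile.

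**The protocol already has a margin.** This stands in part. The k=0.30 scenario can absorb substantial centre variation if the true zone k is near 0.18, and little if it is near 0.28. It was added to cover higher published values of k, not centre sampling, and it does nothing for the lower-k claim. That claim is expressly conditional on the lower k, but not on centres being alike.

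**Months will be pooled.** Monthly data will be analysed with time as a covariate, so a one-month calculation understates the information. This is true, but pooling shrinks the binomial term and leaves persistent centre differences. With six months (n=840, illustrative), k=0.18, kc=0.5 and M large, the detectable reduction is 34.7%, about the one-month figure. The one-level formula at the same n would give 26.0%.

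**Two further inferences do not hold.** A reader might take the remark that published antenatal figures "vary greatly and thus because of the considerable uncertainty in this point estimate" as evidence of large variation between centres. It explains why reference prevalence was varied from 5 to 50% and says nothing about centres within a Sud Ubangi zone. A reader might also think the primary model needs a health-centre random effect. With similar numbers per centre, the zone effect with the planned small-sample correction already absorbs this variance in the arm comparison, so type I error is not the issue.

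**Conclusion.** The omission is real and its direction is certain wherever a zone has more than 7 eligible centres and prevalence differs between them. The detectable reductions are then too small for 80% power. The amount ranges from negligible to material, and the protocol cannot settle where it lies. For 17% prevalence and a between-centre CV of 0.1–0.5, the extreme case with 7 centres a small share of those eligible adds 0.3–7.6 points at k=0.11, 0.3–6.5 at k=0.18 and 0.2–4.7 at k=0.30. With 10 to 15 eligible centres the values become 29.9–34.2%, 34.5–38.1% and 44.2–46.8%. The lower-k statement is the most exposed and the k=0.30 conclusion the least. The robustness sentence goes further than the calculation behind it. This is a shortcoming in the stated precision of the design. It does not invalidate the comparison.

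**What to change.** In the sample size calculation, replace k² by k² + kc²(1−7/M)/7, with M the number of eligible centres in the zone. M can be read from the list used to draw the centres. For kc, either derive a rough proxy from centre-level DHIS2 data or show the range 0.1–0.5, as the protocol already does for k and prevalence. A proxy would be imprecise, because DHIS2 holds no antenatal prevalence and the protocol mentions population estimates only by zone. State M and kc, redraw both curves in Figure 8, and qualify two sentences: the one on detecting the smaller Tanzanian effect at the lower k, and the robustness sentence in the Epidemiology design summary. Reword the remark on random choice of centres so that it claims freedom from selection bias only.

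The cost is a short recalculation and slightly less favourable stated figures. No extra women, centres or zones are needed, and the primary model need not change.

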Results are shown in Figure 8, and suggest that the study design proposed will be capable of detecting a reduction in prevalence of less than the maximum obtained in the Tanzania Olyset + PBO LLIN trial (Protopopoff et al. 2018) even with the higher COV unless prevalence rates are much lower than expected and if the lower COV value is realistic the study has good prospect to detect the lower effect size seen in the Tanzania study with likely prevalence rates. Our data from Nord Ubangi suggest a greater entomological efficacy of Permanet 3 than Olyset + (Figure 3) but it is unclear whether this might translate into a larger epidemiological effect size than

Figure 8. Summary of power for ANC1 prevalence study based on sample size projections of 8 health zones/ arm, 7 health centres/ zone, 20 ANC1 visitors tested per month for two different values of the intercluster coefficient of variation. The plot shows the minimum % reduction in monthly prevalence in PBO vs non-PBO LLIN arms predicted to be detectable (with 80% power) as a function of *Plasmodium* prevalence in ANC1 visitors. Maximum and minimum % reduction estimates obtained in the Tanzania PBO (olyset +) vs standard (olyset) LLIN trial (Protopopoff et al. 2018) are superimposed for context.

obtained in the Tanzania Olyset+ trial. The split zone in Boto could provide one additional non-PBO cluster, if the distribution occurs as planned and can include sufficient health centres, but at present the sample size calculations and power analysis conservatively retain the 8 vs 8 design.

Procedures

ANC visitor recruitment

The recruitment process at each clinic will occur when women attend their first (second trimester) ANC appointment. Women will be asked if they would like to be enrolled in the study, the main

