Nurses at health centres would be responsible for this additional testing and treatment and for the enrolment of participants into the study. Training in administering RDTs and ACTs according to the protocol and filling the register and questionnaires will be organized by the DRC project coordinator

and facilitated by the Gemena-based epidemiological coordinator, in coordination with a representative of the PNLP. It is planned that the training will be conducted in five regional pools to optimize cost and logistical demands. One member of nursing staff per health centre included in the study will be formally trained, along with a representative from each health zone.

Secondary

(*i.e.* to be tested between PBO and non-PBO areas but study not specifically powered for these) RDT-confirmed monthly malaria cases and monthly severe malaria cases per capita. These data will be taken from DHIS2 which is updated monthly for all health centres in relation to population size estimates for each health zone. As noted earlier severe cases are quite rare with approximately 1/20 of the 83,150 malaria cases reported (and confirmed by RDT) in 2018 in the province being recorded as severe.

Epidemiology design summary: 8 zones per LLIN-type arm; 7 health centres per zone; 20 (or more) ANC1 women tested per health centre per month. *Provided the effect size is of the order seen in the Tanzania PBO trial, the design should be robust to variation in currently unknown parameters.*

Data analysis

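### The sample size section derives k = 0.18 but lists k = 0.11 as the power input, with no source; if 0.11 was used, the low-variation detectable reductions are too optimistic

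*Protocol*

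**What the plan says.** All of this is in the protocol's sample size and power text for the primary epidemiological endpoint.

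- The text says of k that it is a quantity "which has a large impact on power".
- Its own estimate, from 2018 DHIS2 positive tests per head as a proxy, is given as: "Following equation 9 in Hayes & Bennett (1999) we calculated k=0.18 from these data".
- It notes that this is lower than the one comparable published study, from Tanzania, with "k values of 0.20-0.28 depending on survey round". For that reason, "we also examined a 'high COV' value of k=0.3".
- The list of inputs to the calculation then reads: "subjects/ cluster = 140; k = 0.11 or 0.30".

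The results are shown only as curves in Figure 8. The text beside the figure says that the higher k still allows detection of a reduction smaller than the Tanzanian maximum, unless prevalence is much lower than expected. For the lower k it says "if the lower COV value is realistic the study has good prospect to detect the lower effect size" seen in Tanzania. The caption mentions two values of the coefficient of variation but does not say what they are.

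**The concern.** The reasoning leads the reader to expect two scenarios: the trial's own estimate of 0.18 and a deliberately high 0.30. The high value is carried into the parameter list correctly and the low one is not. The value 0.11 appears nowhere else, is not derived, and is smaller than every other k in the document.

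With only eight zones per arm, k drives what the trial can detect. The statement that the smaller Tanzanian effect is within reach is tied to the lower value. If that value is 0.11, the favourable scenario assumes less variation between zones than the trial's own data showed. The shortfall could not be made up by adding zones, because the province has 16 and all are used. Whichever value is the mistake, the power statement for the primary endpoint cannot be reproduced as written.

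**Working it through.** **Inputs from the protocol.** 8 zones per arm (c = 8); 7 centres × 20 women = 140 per zone (n = 140); α = 0.05; power 80%; reference prevalence 5-50%, with 17% expected (24% / 1.44 = 16.7%); k = 0.11, 0.18 or 0.30.

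**Assumptions.** The test is two-sided (not stated). The cited Hayes and Bennett equation 4 is taken to be the unmatched formula for proportions:

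c = 1 + (z₀.₉₇₅ + z₀.₈₀)² × [p0(1−p0)/n + p1(1−p1)/n + k²(p0² + p1²)] / (p0 − p1)²

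with (1.960 + 0.842)² = 7.849. It is solved for p1 at c = 8, and the minimum detectable reduction is 1 − p1/p0.

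**The protocol's own figure.** There is no numerical result in the text to reproduce. The results are only in Figure 8, which was not available.

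**Worked case, p0 = 17%.**

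- k = 0.11: p1 = 0.1194. The bracket is 0.001008 + 0.000751 + 0.0121 × 0.04316 = 0.002281, and (p0 − p1)² = 0.002558. Then c = 1 + 7.849 × 0.002281 / 0.002558 = 8.0. The reduction is 29.8%.
- k = 0.18: p1 = 0.1115. The bracket is 0.001008 + 0.000708 + 0.001339 = 0.003055, and (p0 − p1)² = 0.003425. Then c = 1 + 7.849 × 0.003055 / 0.003425 = 8.0. The reduction is 34.4%.

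**Minimum detectable reduction, single month.**

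| Reference prevalence | k = 0.11 | k = 0.18 | k = 0.30 |
|---|---|---|---|
| 5% | 49.8% | 52.1% | 58.0% |
| 10% | 37.2% | 40.7% | 48.8% |
| 17% | 29.8% | 34.4% | 44.2% |
| 30% | 23.6% | 29.6% | 41.0% |
| 50% | 19.5% | 26.7% | 39.1% |

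The step from 0.11 to 0.18 costs about 2 percentage points at 5% prevalence, 4.6 at 17% (34.4 − 29.8), 6.0 at 30% and 7.2 at 50%. Dropping the leading 1 from the formula gives 28.0%, 32.4% and 41.7% at 17% prevalence, so the gap hardly depends on that term.

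**Power at k = 0.18 for the effect that has 80% power at k = 0.11.** At p0 = 17%, the bracket with k = 0.18 and p1 = 0.1194 is 0.001008 + 0.000751 + 0.0324 × 0.04316 = 0.003157. Then √(7 × 0.002558 / 0.003157) = 2.381; 2.381 − 1.960 = 0.421; and Φ(0.421) = 66%. The same steps give 71% at 10% prevalence, 59% at 30% and 51% at 50%. A noncentral t calculation with 14 degrees of freedom gives 66% at 17% prevalence and 58% at 30%.

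**Zones needed.** At 17% prevalence, detecting the 29.8% reduction with k = 0.18 needs c = 1 + 7.849 × 0.003157 / 0.002558 = 10.7, so 11 zones per arm instead of 8.

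**The case against.** The strongest reply is that nothing shows 0.11 was ever used. The narrative describes two scenarios, 0.18 and 0.30, and 0.11 could be a misprint or a leftover in the list. The lower curve may then already be correct. The error could also lie in the 0.18. This stands. A reader might infer that the protocol's detectable reductions are too optimistic, but the text states none and the caption gives no k values, so the optimism is conditional.

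Three further points stand in part.

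- The k = 0.30 scenario is intact. It exceeds both 0.18 and the whole Tanzanian range, so the conclusion drawn from it does not change and a further curve at 0.28 is not needed.
- The sentence about the smaller effect is explicitly conditional on the lower value being realistic. A reader might infer that it fails at k = 0.18. The Tanzanian effect sizes are not given as numbers, so this cannot be tested from the document.
- A reader might infer that the design summary's statement that "the design should be robust to variation in currently unknown parameters" is also wrong. It is conditioned on an effect of the Tanzanian order, and nothing shows that it rests on 0.11 rather than on the 0.30 scenario.

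It is also fair to say that these figures describe a single month, as the protocol's own power calculation does, and not the planned analysis of all months with time as a covariate.

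None of this removes the contradiction between the two values.

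**Conclusion.** The protocol is inconsistent on the input that it singles out as important for power: 0.18 is calculated, 0.11 is listed, and nothing links them. That is certain from the text.

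The effect on the results is conditional. If 0.11 generated the lower curve, the low-variation detectable reductions are too small by about 2 to 7 percentage points over the 5-50% prevalence range. The smallest effect detectable with 80% power at 0.11 would have about 66% power at the expected 17% prevalence, and 58-59% at 30%. If 0.11 is a misprint for 0.18, the curve is right and only the list is wrong. The figures rest on the unmatched Hayes and Bennett formula, a two-sided 5% test and a single month's data.

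The documents do not support the broader reading that the trial as a whole is underpowered or that the higher-variation conclusion fails.

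**What to change.** State which k produced the lower curve, and print both k values in the Figure 8 caption. Then:

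- If it was 0.11, rerun at k = 0.18, redraw the lower curve, restate the low-variation detectable reduction (about 34% at 17% prevalence), and recheck the sentence on the smaller Tanzanian effect against it, giving that effect as a number.
- If 0.11 is a misprint, correct the parameter list to 0.18.
- If 0.18 is the error, correct it and give the derivation of 0.11.

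The cost is one corrected number or one redrawn curve with its accompanying sentence. Design, conduct and analysis are unchanged. In the first case the stated detectable effect becomes less favourable.
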